7.1.1 Study Definitions

Duration of exposure to double-blind study drug (days) :

Date of last dose of double-blind study drug - date of first dose of double-blind study drug +
1

Double-blind study drug compliance (%) :

Number of TAK-385 blinded drugs taken/duration of exposure to TAK-385 blinded drug *
100 (rounded to 1 decimal places)

Disease duration (years):

((year of informed consent*12 + month of informed consent) -(year of first defined diagnosis of uterine fibroids*12 + month of first defined diagnosis of uterine fibroids))/12 (rounded to 1 decimal places)

Maximum drug holidays (days):

Maximum number of consecutive days on which the subject does not take the TAK-385 blinded drug for the treatment period

Total PBAC score from Week 6 to 12

Total PBAC score from Day 43 to earlier of Day 84 or Follow-up Day 3.

Similarly, Total PBAC score from Week 2 to 6 and from Week 18 to 24 will be defined as

those from Day 15 to earlier of Day 42 or Follow-up Day 3 and from Day 127 to earlier of Day 168 or Follow-up Day 3, respectively.

Total PBAC score for 6 weeks before the final dose of study drug

Total PBAC score for the last 42 days of the treatment

NRS score from Week 6 to 12

Average NRS score from Day 43 to earlier of Day 84 or Follow-up Day 3.

Similarly, NRS score from Week 2 to 6 and from Week 18 to 24 will be defined as average NRS score from Day 15 to earlier of Day 42 or Follow-up Day 3 and from Day 127 to earlier of Day 168 or Follow-up Day 3, respectively.

NRS score for 6 weeks before the final dose

Average NRS score for the last 42 days of the treatment

Total PBAC at baseline

Total PBAC score from first day of menstrual period confirmed at Visit 2 to a day prior to menstrual period confirmed at Visit 3

NRS score at baseline

Average NRS score from first day of menstrual period confirmed at Visit 2 to a day prior to menstrual period confirmed at Visit 3

Use of analgesic medications during the treatment from Week 6 to 12

((number of days with analgesic medications use between Day 43 and earlier of Day 84 or Follow-up Day 3)/(number of days with available data between Day 43 and earlier of Day 84 or Follow-up Day 3))*100 (rounded to 1 decimal places)

Similarly, use of analgesic medications during the treatment from Week 2 to 6 and from Week 18 to 24 will be defined as proportion of days with analgesic use between Day 15 and earlier of Day 42 or Follow-up Day 3 and between Day 127 and earlier of Day 168 or Follow-up Day 3, respectively.

Use of analgesic medications during the Treatment for 6 weeks before the final dose

((number of days with analgesic medications use for the last 42 days of the treatment)/(number of days with available data for the last 42 days of the treatment))*100 (rounded to 1 decimal places)

Proportion of subjects with a total PBAC score of < 10 from Week 6 to 12:

((number of subjects with a total PBAC score of less than 10 from Week 6 to 12)/(number of subjects with available PBAC score from Week 6 to 12))*100 (rounded to 1 decimal places)

Myoma volumes

$D1*D2*D3*\pi/6$ (cm³)

Uterine volumes will be similarly calculated.

Definitions of D1, D2 and D3 are shown in protocol.

Duration of Menstruation Recovery

Date of menstruation recovery - date of last dose of double-blind study drug

Oral iron preparation

The drug with the following drug code of WHODD:
00023503001, 00023505001, 00023520001, 00023550009, 00023550074, 90059601001

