13.1.1 Analysis Sets

In this study, three kinds of analysis sets are defined: full analysis set (FAS), per protocol set (PPS) and safety analysis set. The FAS, the main analysis set used for primary efficacy analysis, will be defined as "all subjects who were randomized and received at least one dose of the study drug." The definition of each analysis set will be described in the Handling Rules for Analysis Data.

The sponsor will verify the validity of the definitions of the analysis sets as well as the rules for handling data, consulting a medical expert as needed. If necessary, the Handling Rules for Analysis Data will be supplemented with new handling rules that were not discussed at the planning stage. The Handling Rules for Analysis Data must be finalized prior to database lock.

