7.0 METHODS OF ANALYSIS AND PRESENTATION

7.1 General Principles

All statistical analyses will be conducted using SAS® Version 9.2, or higher.

A statistical test for the primary endpoint will be reported as 1-sided and will be assessed at $\alpha=0.025$ significance level and all confidence intervals will be reported as 2-sided unless otherwise stated. P-values will be rounded to 4 decimal places prior to assessment of statistical significance.

Means and medians will be presented to 1 more decimal place than the recorded data. The standard deviations (SDs) will be presented to 2 more decimal places than the recorded data. Confidence intervals about a parameter estimate will be presented using the same number of decimal places as the parameter estimate.

Where appropriate, variables will be summarized descriptively by study visit. For the categorical variables, the count and proportions of each possible value will be tabulated by treatment group. The denominator for the proportion will be based on the number of subjects who provided non-missing responses to the categorical variable. For continuous variables, the number of subjects with non-missing values, mean, median, SD, minimum, and maximum values will be tabulated. Confidence intervals for continuous variables will be calculated based on t-statistics and ones for categorical variables will be based on Wald confidence intervals without using any model, unless otherwise stated.

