7.1.2 Definition of Study Days

When calculating Study Day relative to a reference date (ie, date of first dose of double-blind study drug [Day 1]) , if the date of the observation is on the same date or after the reference date, it will be calculated as: date of observation - reference date + 1; otherwise, it will be calculated as: date of observation - reference date. Hence, reference day is always Day 1 and there is no Day 0.

When calculating Follow-up Day relative to a reference date (ie, date of last dose of double-blind study drug [Follow-up Day 0]) , it will be calculated as: date of observation - reference date. Hence, reference day is always Follow-up Day 0.

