7.1.4 Methods for Handling Missing Data

All available efficacy and safety data will be included in data listing and tabulations. No imputation of values for missing data will be performed unless otherwise specified.

- For UFS-QoL and WPAI, published scoring manuals and guidelines will be used to calculate UFS-QoL and WPAI scale scores and handle missing data (see Appendix 3 and 4, respectively).
- For myoma or uterus volume, if D1 and D2 of the myoma or uterus are present but D3 is missing, then the volume will be calculated as $D1*D2*D2*\pi/6$ (cm^3).
- For LH, FSH, E₂, P and clinical laboratory tests, values less than the lower limit of quantification will be treated as zero when calculating the descriptive statistics.
- Disease duration with first diagnosis date of uterine fibroid that are completely or partially missing will be derived as follows:
 1. If the year is missing, then the disease duration will be treated as missing.
 2. If the year is present but the month is missing, then the month will be treated as January for the calculation.

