7.8 Efficacy Analysis

7.8.1 Primary Efficacy Endpoint(s)

7.8.1.1 Primary Analysis

Analysis Set: Full Analysis Set

Analysis

Variable(s): Proportion of subjects with a total PBAC score of < 10 from Week 6 to 12

Analytical Method(s): The point estimate and 2-sided 95% confidence interval of the proportion of subjects with a total PBAC score of < 10 from Week 6 to 12 will be summarized by treatment group. The point estimate and 2-sided 95% confidence interval of the difference in the percentage will be calculated between TAK-385 40 mg group and leuprorelin group (TAK-385 40 mg group – leuprorelin group), using Farrington and Manning (FM) method. In addition, non-inferiority test using FM method with a non-inferiority margin of 15% will be conducted for the comparison between TAK-385 40 mg group and leuprorelin group. If the lower bound of the 95%CI is greater or equal to the non-inferiority margin of -15%, then non-inferiority of TAK-385 40mg to leuprorelin will be concluded.

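### A Week 6–12 PBAC total cut short by early stopping counts as response if below 10, subjects with no score leave the FAS denominator, and no planned analysis varies either group's outcome

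*SAP*

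**What the plan says.** SAP 7.1.1 sets the primary score as "Total PBAC score from Day 43 to earlier of Day 84 or Follow-up Day 3". SAP 7.1.2 fixes the reference point for Follow-up Days as the "date of last dose of double-blind study drug [Follow-up Day 0"]. The score is a sum. In the same section the NRS score is an average, and analgesic use is divided by the days with data.

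A subject with a total below 10 is a responder, and the divisor is the "number of subjects with available PBAC score from Week 6 to 12". SAP 7.1 gives the same general rule: "The denominator for the proportion will be based on the number of subjects who provided non-missing responses to the categorical variable". SAP 7.1.4 adds: "No imputation of values for missing data will be performed unless otherwise specified". None of the exceptions listed there concerns PBAC.

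The primary analysis (SAP 7.8.1.1) carries the label "Analysis Set: Full Analysis Set". Protocol 13.1.1 defines that set as "all subjects who were randomized and received at least one dose of the study drug", with no requirement for a post-baseline score. It also says: "The definition of each analysis set will be described in the Handling Rules for Analysis Data". Those Handling Rules are not among the documents available. Protocol 13.1.3 (4) sends the handling of missing data to the SAP.

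**The concern.** Protocol 6.2.3.1 chose a 6-week window so that it would span the longest normal cycle, 38 days. A sum over a shorter window can only be the same or smaller. A partial total of 10 or more therefore proves failure, but a partial total below 10 does not prove response over six weeks. The rule as written treats both as settled.

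Early leavers are also unlikely to be a random sample. Protocol 7.5 lists lack of efficacy and hemoglobin below 8.0 g/dL, both likely to be tied to bleeding. It also lists leaving for surgery after recovery, which requires a favorable outcome. If the arms differ in how many leave or in why they leave, the non-inferiority comparison can shift in either direction.

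The planned checks do not test this:

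- The PPS repeat (SAP 7.8.1.2), the baseline-adjusted model (7.8.1.3) and the subgroups (7.8.1.4) all reuse the same response variable.
- The endpoint for the last 42 days of treatment (7.8.2.1) uses a different window and is descriptive.

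**Working it through.** **The plan's own figures.** Inputs from SAP 6.0: 83.6% in both arms, margin 15 points, 1-sided 0.025, power 90%.

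n = (1.960 + 1.282)² × 2 × 0.836 × 0.164 / 0.15² = 128.05, rounded up to 129. Then 129 / 0.90 = 143.3, rounded up to 144. Both figures reproduce. The 10% allowance shows that a reduced denominator was intended.

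**Window length.** With last dose on Day L, the days in the window are min(84, L + 3) − 42.

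| Last dose | Days counted |
|---|---|
| Day 39 | 0 |
| Day 40 | 1 |
| Day 56 | 17 |
| Day 80 | 41 |
| Day 81 or later | 42 |

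These are calendar days. Under Protocol 9.1.16 the diary runs only to early termination, so the three days after the last dose may have no entries.

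**Effect on the test.** True rates are set at the margin: 68.6% on TAK-385 and 83.6% on leuprorelin, 144 per arm. The probability of passing the Farrington–Manning test (z ≥ 1.96) is summed exactly over both binomial distributions. With no loss it is 2.5%. Loss by arm and the share of leavers who are failures are assumptions, because the documents give only about 10% not evaluable overall.

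*Empty windows dropped.* With loss e and failure share f, the displayed rate is (p − e(1 − f)) / (1 − e) on n = 144 − round(144e). Example with 10%/5% loss, all failures: 0.686/0.90 = 76.2% on 130, against 0.836/0.95 = 88.0% on 137. The displayed difference is −11.8 points instead of −15.

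| Loss TAK-385 / leuprorelin | Failure share TAK-385 / leuprorelin | False non-inferiority |
|---|---|---|
| 10% / 5% | 100% / 100% | 10.2% |
| 10% / 5% | 75% / 75% | 5.6% |
| 10% / 5% | 50% / 50% | 2.9% |
| 4% / 2% | 75% / 75% | 3.4% |
| 5% / 3% | 75% / 75% | 3.1% |
| 3% / 3% | 75% / 75% | 2.0% |
| 5% / 5% | 100% / 100% | 1.7% |
| 10% / 10% | 100% / 100% | 1.0% |
| 3% / 3% | 100% / 50% | 4.1% |
| 5% / 5% | 100% / 50% | 5.7% |
| 10% / 10% | 100% / 50% | 12.7% |
| 5% / 10% | 100% / 100% | 0.06% |
| 5% / 10% | 75% / 75% | 0.22% |
| 5% / 10% | 50% / 50% | 0.6% |
| 5% / 5% | 50% / 100% | 0.38% |
| 10% / 10% | 50% / 100% | 0.02% |

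*Short windows counted as response.* With k failures scored as responders in the TAK-385 arm only, its rate becomes 0.686 + k/144. For k = 1, 2 or 3 the result is 3.5%, 4.7% or 6.3%. The same k in both arms leaves it at 2.5%.

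*Counting leavers as non-response.* The rate is p − e(1 − f) on 144. At 10%/10% loss with failure shares 100%/50%, the rates are 68.6% and 83.6% − 5.0% = 78.6%. The displayed difference is −10.0 points and false non-inferiority is 16.3%. At 5%/10% with half failures it is 7.0%, against 0.6% with the SAP denominator.

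**One data set.** Take 108/129 responders in each arm, with 15 per arm missing.

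- As planned: z = 3.15.
- All missing counted as non-response, 108/144 in each arm: z = 2.93.
- All 15 TAK-385 leavers fail and 8 of 15 leuprorelin leavers respond, 108/144 against 116/144: z = 1.93, and non-inferiority is lost.
- The same with 7 of 15 responding, 108/144 against 115/144: z = 2.06, and non-inferiority holds.

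**The case against.** The strongest reply is that the denominator is open and deliberate. SAP 6.0, 7.1 and 7.1.1 agree on it, and the trial was sized for it. That stands: this is a disputable choice, not a hidden one. But the allowance protects power, not against informative loss.

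Second, the Handling Rules may define when a score is available, and Protocol 13.1 plans a blinded review of subject evaluability. A diary minimum may therefore exist. That limits the truncation point to the text of the SAP. However, the protocol assigns missing data to the SAP, and its change log records edits made after blind review without adding a PBAC rule. A minimum that excluded short diaries would also enlarge the dropped group.

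Third, the bias may run against TAK-385. Protocol 4.1 describes flare-up and a 3 to 4 week delay with GnRH agonists, and faster onset without flare-up for TAK-385. Bleeding-related exits before Day 40 could then fall more on leuprorelin, which gives the results below 1% in the table. Milder contrasts also matter little: failure shares of 75% against 50% give 2.9% at 3%/3% loss and 3.2% at 5%/5%. This stands, and no direction is claimed.

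Fourth, the last-42-days endpoint can give a full window to nearly everyone whose Week 6–12 window is truncated. It is a useful partial check. For early stoppers, though, it reaches back into the onset period, and it does not address the Week 6–12 outcome.

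**Conclusion.** The concern holds for the SAP as written, and it should be fixed before unblinding. One diary day can stand for a six-week response, leavers without a score vanish from an analysis labelled FAS, and nothing planned shows whether the conclusion survives other outcomes for them.

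The size depends on assumed losses. Balanced loss for balanced reasons was conservative in the cases computed, at 1.0% to 2.0%. A material rise above 2.5% needs the arms to differ in loss or in reasons for stopping; the largest value computed with the SAP denominator was 12.7%. These figures show sensitivity and do not predict the result. Confidence is medium, because the Handling Rules are unseen and the documents give no loss by arm.

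**What to change.** Before unblinding:

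1. In SAP 7.1.1, state that an observed total of 10 or more is non-response whatever the window length, and that a total below 10 from an incomplete window is not automatically response. Set the completeness rule at blinded review. Repeat in the SAP any diary minimum, and the handling of missed diary days, from the Handling Rules. State the corresponding rule for the Week 2–6 and Week 18–24 windows.
2. The planned primary denominator may stay. In SAP 7.8.1, add two sensitivity analyses on all FAS subjects: (a) empty windows, and incomplete windows with a total below 10, counted as non-response; (b) a tipping-point analysis that varies their outcome separately by arm, including those who left for surgery after recovery. Analysis (b) is needed because (a) alone can also favor non-inferiority.
3. Extend the exclusion tables of SAP 7.3.7 to show incomplete and empty windows by arm and reason for stopping.

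The cost is SAP wording and some programming, with no new data and no loss of power. If non-response counting were made primary instead, power at 144 per arm would need restating: from 92.5% with no loss to 88.1% if 5% per arm are lost and counted as failures, or 84.1% if 10% are.

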7.1.2 Definition of Study Days

When calculating Study Day relative to a reference date (ie, date of first dose of double-blind study drug [Day 1]) , if the date of the observation is on the same date or after the reference date, it will be calculated as: date of observation - reference date + 1; otherwise, it will be calculated as: date of observation - reference date. Hence, reference day is always Day 1 and there is no Day 0.

When calculating Follow-up Day relative to a reference date (ie, date of last dose of double-blind study drug [Follow-up Day 0]) , it will be calculated as: date of observation - reference date. Hence, reference day is always Follow-up Day 0.

7.1.3 Definition of Study Visit Windows

All evaluable data (ie, non-missing and acceptable according to the Handling Rules for Analysis Data) will be handled according to the following rules.

For each visit, observation obtained in the corresponding time interval will be used. If more than one observation lies within the same visit window, the observation with the closest Study Day to the scheduled Study Day will be used. If there are two observations equidistant to the scheduled Study Day, the later observation will be used.

Transvaginal ultrasound and WPAI

Visit	Scheduled Study Day (days)	Time Interval (days)	
		Study Day	Follow-up Day
Baseline	Study Day: 1	-80 - 1	
Week 2	Study Day: 15	2 - 22	< 4
Week 4	Study Day: 29	23 - 43	< 4
Week 8	Study Day: 57	44 - 71	< 4
Week 12	Study Day: 85	72 - 127	< 4
Week 24	Study Day: 169	128 – 183	< 4

Anemia-related measurements (Hemoglobin [HGB], Hematocrit [HCT], Serum Fe, and Serum Ferritin) and UFS-QOL score

Visit	Scheduled Study Day	Time Interval (days)
-------	---------------------	----------------------

	(days)	Study Day	Follow-up Day
Baseline	Study Day: 1	-80 - 1	
Week 4	Study Day: 29	2 – 43	< 4
Week 8	Study Day: 57	44 – 71	< 4
Week 12	Study Day: 85	72 – 99	< 4
Week 16	Study Day: 113	100 – 127	< 4
Week 20	Study Day: 141	128 – 155	< 4
Week 24	Study Day: 169	156 – 183	< 4
Follow-up	Follow-up Day: 28	2 <=	4 – 42

Clinical laboratory tests (except bile acid (total bile acid [TBA]) and glutamate dehydrogenase (GLDH)) and vital sign and weight

Visit	Scheduled Study Day (days)	Time Interval (days)	
		Study Day	Follow-up Day
Baseline	Study Day: 1	-80 - 1	
Week 4	Study Day: 29	2 – 43	< 15
Week 8	Study Day: 57	44 – 71	< 15
Week 12	Study Day: 85	72 – 99	< 15
Week 16	Study Day: 113	100 – 127	< 15
Week 20	Study Day: 141	128 – 155	< 15
Week 24	Study Day: 169	156 – 183	< 15
Follow-up	Follow-up Day: 28	2 <=	15 – 42

Pharmacodynamic measurements

Visit	Scheduled Study Day (days)	Time Interval (days)	
		Study Day	Follow-up Day
Baseline	Study Day: 1	-80 - 1	
Week 2	Study Day: 15	2 – 22	< 4
Week 4	Study Day: 29	23 – 43	< 4
Week 8	Study Day: 57	44 – 71	< 4
Week 12	Study Day: 85	72 – 99	< 4
Week 16	Study Day: 113	100 – 127	< 4

Visit	Scheduled Study Day (days)	Time Interval (days)	
		Study Day	Follow-up Day
Week 20	Study Day: 141	128 – 155	< 4
Week 24	Study Day: 169	156 – 183	< 4
Follow-up	Follow-up Day: 28	2 <=	4 – 42

Clinical laboratory tests (TBA and GLDH)

Visit	Scheduled Study Day (days)	Time Interval (days)	
		Study Day	Follow-up Day
Baseline	Study Day: 1	-80 - 1	
Week 2	Study Day: 15	2 – 22	< 15
Week 4	Study Day: 29	23 – 43	< 15
Week 8	Study Day: 57	44 – 71	< 15
Week 12	Study Day: 85	72 – 99	< 15
Week 16	Study Day: 113	100 – 127	< 15
Week 20	Study Day: 141	128 – 155	< 15
Week 24	Study Day: 169	156 – 183	< 15
Follow-up	Follow-up Day: 28	2 <=	15 – 42

12-lead ECG

Visit	Scheduled Study Day (days)	Time Interval (days)	
		Study Day	Follow-up Day
Baseline	Study Day: 1	-80 - 1	
Week 24	Study Day: 169	2 – 183	< 15
Follow-up	Follow-up Day: 28	2 <=	15 – 42

Biochemical bone metabolism markers and BMD

Visit	Scheduled Study Day (days)	Time Interval (days)	
		Study Day	Follow-up Day
Baseline	Study Day: 1	-80 - 1	

Visit	Scheduled Study Day (days)	Time Interval (days)	
		Study Day	Follow-up Day
Week 12	Study Day: 85	2 – 127	< 15
Week 24	Study Day: 169	128 – 183	< 15

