4. Lost to follow-up. The subject did not return to the clinic and attempts to contact the subject were unsuccessful. Attempts to contact the subject must be documented.
5. Withdrawal by subject. The subject wishes to withdraw from the study. The reason for withdrawal, if provided, should be recorded in the eCRF.

Note: All attempts should be made to determine the underlying reason for the withdrawal and, where possible, the primary underlying reason should be recorded (withdrawal due to an AE or lack of efficacy should not be recorded in the "Withdrawal by subject" category). If subject wishes to withdraw from the study to proceed to surgery, the category No.9 "Recovery leading to surgery" should be recorded.

6. Study terminated by sponsor. The sponsor terminates the study.
7. Pregnancy. The subject is found to be pregnant.

Note: If the subject is found to be pregnant, the subject must be withdrawn immediately. The procedure is described in Section 9.1.10.

8. Lack of efficacy. The investigator or subinvestigator judges TAK-385 shows no efficacy based on the menstrual blood loss, menstrual status, and use of analgesics (eg, a notable increase in menstrual blood loss after start of study drug administration) and judges continued participation in the study would pose an unacceptable risk to the subject.

9. Bone mineral density loss. The subjects with BMD measured by DXA at VISIT 7 is $< 90\%$ of baseline (or subjects with BMD changes from baseline $> 10\%$), or the investigator or subinvestigator makes an overall risk-benefit assessment for the subject and decides to stop the study drug administration, even if the subject's BMD maintains $\geq 90\%$ of baseline (or with a BMD change from baseline $\leq 10\%$).
10. Recovery leading to surgery. The subject who does not apply to any of the above category 1 to 8 and has a favorable outcome (eg, the improvement in the bleeding profile, the reduction in myoma and uterine volumes, and improvement in anemia) leading to the proceeding to surgery, and the investigator or subinvestigator judges that it is appropriate to proceed to surgery and not ethically desirable for the subject to be administered the study drug any longer.
11. Reduction of HGB concentration. Regardless of with or without iron preparations administration, HGB concentration of subject at VISIT 2 or later decreases to < 8.0 g/dL.
12. Other.

Note: The specific reasons should be recorded in the "specify" field of the eCRF.

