9.3.3 Final Visit or Early Termination

9.3.3.1 VISIT 10 (Day 169) (or Early Termination)

The final visit during the Treatment will be performed on VISIT 10 (169 days after the initial dose of the study medication for the Treatment). The following procedures should be performed. If early termination occurs during the Treatment, the same procedures scheduled at VISIT 10 should be performed.

- Pregnancy test (urine)
- Physical examination
- Vital signs and weight
- Patient diary (collected)
- Transvaginal ultrasound (see Section 9.1.17).
- BMD
- UFS-QOL
- WPAI:GH
- Anemia-related measurements
- Clinical laboratory tests

- Pharmacodynamic measurements
- Biochemical bone metabolism markers
- Standard 12-lead ECG
- AE
- Concomitant medications
- Compliance of study drug administration
- PGx sample collection (perform only in subjects who consent and from whom the sample has not been collected [see Section 9.1.12])

For all subjects receiving study medication, the investigator or subinvestigator must complete the Subject Status eCRF page.

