7.11.2 Clinical Laboratory Evaluations

7.11.2.1 Hematology and Serum Chemistry

Analysis Set: Safety Analysis Set

Analysis

Variable(s) : Hematology

RBC	Platelets	WBC
WBC Differentials (Neutrophils, Eosinophils, Basophils, Lymphocytes, Monocytes)		

Serum Chemistry

ALT	AST	Lactate dehydrogenase (LDH)
Gamma glutamyl transferase (GGT)	Albumin	Alkaline phosphatase (ALP)
Bilirubin (Total bilirubin)	Protein (Total protein)	Cholesterol (Total cholesterol)
High density lipoprotein (HDL) cholesterol	Low density lipoprotein (LDL) cholesterol	Triglycerides
Glucose	HGB A1C	Creatinine
Blood urea nitrogen (BUN)	Creatine kinase	Urate
Sodium	Potassium	Chloride
Calcium	Phosphate	Magnesium
Bile acid (total bile acid [TBA])	Glutamate dehydrogenase (GLDH)	

Visit: Baseline, Week 2*, 4, 8, 12, 16, 20, 24 and Follow-up

*: only TBA and GLDH

Analytical

Method(s) : For each variable, summaries (1) to (3) will be provided by treatment group.
For applicable variables, summaries (4) and (5) will be provided by treatment group.

- (1) Summary of Laboratory Test Results and Change from Baseline by Visit
Descriptive statistics for observed values for each visit and changes from baseline will be provided.
- (2) Case Plots
Plots over time for each subject will be presented.
- (3) Summary of Shifts of Laboratory Test Results
Shift tables showing the number of subjects in each category at baseline and each post-baseline visit will be provided.
For each laboratory test, the laboratory values will be classified as "Low", "Normal" or "High" relative to the normal reference range provided by the central laboratory. The shift tables will be based on these classifications.
- (4) Number and Percentage of Subjects with Markedly Abnormal Values of Laboratory Parameters
Overall frequency distributions of MAV during treatment period will be provided. If a laboratory parameter has both lower and upper MAV criteria, analysis will be performed for each. Further details are given in Appendix.
- (5) Number and Percentage of Subjects with Elevated Liver Enzyme Laboratory Parameters
Overall frequency distributions of elevated hepatic parameters during treatment period will be provided. Further details are given in Appendix.

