7.11.5 Other Observations Related to Safety

7.11.5.1 Bone Mineral Density and Biochemical Bone Metabolism Markers

Analysis Set: Safety Analysis Set

Analysis

Variable(s) : T score [Min <= -2.500,

-2.499<= - <=-1.000,
-0.999<= - <= MAX]

Bone Mineral Density (g/cm²)

Percent Change from baseline on Bone [Min<= - <-7, -7<= - <=Max]

Mineral Density (%)

NTELOP (nmol BCE/L)

Bone Type Alkaline Phosphatase (μg/L)

Visit: Baseline , Week 12, 24

Analytical

Method(s) : For each variable except T score, summaries (1), (3), and (4) will be provided by treatment group.

For T score, summary (2), (3), (4), and (5) will be provided by treatment group.

(1) Summary of Parameters and percent Change from Baseline by Visit
Descriptive statistics for observed values for each visit and percent changes from baseline will be provided.
For categorical variables, frequency will be summarized by treatment group for each visit.

(2) Summary of Parameters and Change from Baseline by Visit
Descriptive statistics for observed values for each visit and changes from baseline will be provided.

(3) Case Plots
Plots over time for each subject will be presented.

(4) Mean Plot with Standard Deviations
For T score, mean of observed values and changes from baseline will be plotted by visit.
For other variables, mean of observed values and percent changes from baseline will be plotted by visit.

(5) Summary of Shift of T score
Shift table showing the number of subjects in each category at baseline and each post-baseline visit will be provided.

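### A DXA taken at early termination on Day 86–127 normally drops out of every BMD summary table, and no planned table gives the number of women per arm who ever lost more than 7%

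*SAP*

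**What the plan says.** - **Scans.** DXA is done between VISIT 2 and VISIT 3, at VISIT 7 (Day 85) and at VISIT 10 (Day 169). For women who stop early, Protocol 9.3.3.1 says "If early termination occurs during the Treatment, the same procedures scheduled at VISIT 10 should be performed"; those procedures include BMD.
- **Withdrawal for bone loss.** Protocol 7.5 item 9 begins "Bone mineral density loss. The subjects with BMD measured by DXA at VISIT 7 is" under 90% of baseline. It also lets the investigator stop study drug for a smaller loss.
- **Windows.** The SAP 7.1.3 table headed "Biochemical bone metabolism markers and BMD" sets Week 12 as Day 2–127 (target Day 85) and Week 24 as Day 128–183 (target Day 169). Both require Follow-up Day below 15, that is, a scan no more than 14 days after the last dose.
- **Choice within a window.** "If more than one observation lies within the same visit window, the observation with the closest Study Day to the scheduled Study Day" is the one used. On ties: "If there are two observations equidistant to the scheduled Study Day, the later observation will be used".
- **Tables.** SAP 7.11.5.1 splits BMD percent change at -7%, and "For categorical variables, frequency will be summarized by treatment group for each visit". The descriptive statistics, mean plots and T-score shift table are also by visit. Case plots are planned for each subject.
- **Denominators and missing data.** Percentages use women with a non-missing value (SAP 7.1). Missing values are not imputed, and all data go into listings (SAP 7.1.4).
- **Other parameters.** For laboratory tests SAP 7.11.2.1 adds a count over the whole period: "Overall frequency distributions of MAV during treatment period will be provided". SAP 7.11.3.1 does the same for vital signs. The ECG Week 24 window runs from Day 2 to Day 183, and PBAC, NRS and analgesic use each have a measure over the last 42 days of treatment. BMD has no comparable summary.

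**The concern.** Protocol 6.2.1 gives the comparison of BMD with GnRH agonists as one reason for the 24-week treatment period, so the Week 24 bone table will be read as a main safety result. That table includes only women scanned on Day 128 or later. One route out of it is withdrawal for bone loss itself, so missingness at Week 24 depends on the outcome being measured. If one arm loses more bone early, more of its women leave the Week 24 numerator and denominator.

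The woman's last scan under treatment, which best describes her state when she stopped, is the one the window rule passes over. A reader who wants the number of women per arm who ever lost more than 7% will find it in no planned table.

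**Working it through.** The plan states no figure on this point to reproduce. The check has two parts: the window logic, which rests on the text, and an estimate of size, which rests on assumptions.

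**Window logic**

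1. A VISIT 7 scan on Day 85 is 0 days from target. An early-termination scan on Day d, with d from 86 to 127, is d - 85 days away, which is at least 1. The VISIT 7 scan wins every time, and the tie rule never applies.
2. A scan dated by Day 127 cannot enter Week 24, and nothing is imputed, so Week 24 is empty for that woman. The Day 127/128 boundary removes her from Week 24; the closest-day rule removes the scan from Week 12. The scan leaves the tables only because both apply.
3. What matters is the scan date, not the stop date. A woman whose last dose is on Day 114–127 and who is scanned on Day 128 or later, within 14 days, enters Week 24.
4. Last-dose days 86–127 (42 values) crossed with scan lags of 0–14 days (15 values) give 42 × 15 = 630 combinations. With VISIT 7 on Day 85, the early-termination scan is displaced in 525 (83%) and enters Week 24 in 105 (17%). These are shares of calendar combinations, not of women.
5. The documents give no visit tolerance, so the VISIT 7 scan date was varied. On Day 78 or 82, the early-termination scan replaces the VISIT 7 scan at Week 12 in 4% or 1% of combinations. On Day 88 or 92, it is displaced in 82% or 80%. With no VISIT 7 scan, the early-termination scan is used at Week 12.

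**Size**

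The documents give no BMD mean, SD or stopping rate, so every input here is an assumption. Percent changes at Weeks 12 and 24 are bivariate normal with correlation 0.6. Women below -10% at Week 12 stop, and a further 5% or 10% stop at random. The early-termination scan falls uniformly on Day 86–127, with BMD interpolated linearly. Results are from simulation, per 144 women in an arm.

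| Mean (SD) Week 12; Week 24; other stops | Stopped | Below -7% at Week 24 | Below -7% at any scan | >7% loss, absent from Week 24 | of these, shown at Week 12 | of these, only on displaced scan | Completers below -7% at Week 12 only |
|---|---|---|---|---|---|---|---|
| -2.5 (3); -4.5 (3.5); 5% | 8.1 | 31.6 | 35.8 | 1.5 | 1.3 | 0.2 | 2.6 |
| -2.5 (3); -4.5 (3.5); 10% | 15.2 | 30.1 | 34.7 | 2.1 | 1.7 | 0.4 | 2.5 |
| -3.5 (3); -5.5 (3.5); 5% | 9.3 | 43.8 | 51.1 | 3.2 | 2.9 | 0.3 | 3.9 |
| -3.5 (4); -6 (4.5); 10% | 21.2 | 47.4 | 62.6 | 10.2 | 9.5 | 0.7 | 4.9 |

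The any-scan count is the Week 24 count, plus those absent, plus completers below -7% at Week 12 only. In the last row 47.4 + 10.2 + 4.9 = 62.5, against 62.6; all rows agree within 0.2, which is simulation and rounding error.

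**Why the visit counts cannot be added**

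In the first row the expected Week 12 count is 144 × Φ((-7 + 2.5)/3) = 144 × Φ(-1.5) = 144 × 0.0668 = 9.6. Adding Week 24 gives 9.6 + 31.6 = 41.2, against 35.8 women who ever fell below -7%. The sum counts women below -7% at both visits twice, and the planned tables do not show how many there are.

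**The case against.** The strongest reply is that the women of most concern are already visible. Item 9 acts on the VISIT 7 scan, and with that scan on Day 85 it is the one the rule keeps. A woman below 90% of baseline there counts as below -7% at Week 12, by arm. SAP 7.3.5 also tabulates bone mineral density loss as a reason for discontinuation, by arm. A reader might infer that the plan hides bone loss in withdrawn women; the documents do not support that. The partial exception is a woman withdrawn at the investigator's discretion with a loss of 7% or less at VISIT 7: disposition shows her, but the below -7% category does not.

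Two further replies stand:

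- A woman who stopped around Day 95 has no 24-week exposure, and her absence from Week 24 is correct. Protocol 13.1.5 asks for by-visit BMD summaries and case plots, and the SAP delivers them.
- Most of the gap between the any-scan and Week 24 counts does not come from displaced scans. It comes from completers whose loss was below -7% only at Week 12 (2.5–4.9 per arm) and from stopped women already shown at Week 12.

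A reader might also take every woman who stops between VISIT 7 and Day 127 to be lost from Week 24, which step 3 of the window check rules out. Nor do the documents rank BMD as the main known harm: LFT abnormality is the only adverse event of special interest named.

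What these replies leave untouched is the missing summary. Neither visit table, nor both together, gives the number who ever lost more than 7% or BMD at the end of each woman's treatment.

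**Conclusion.** The point holds as a modest gap in safety reporting. An early-termination DXA on Day 86–127 is normally displaced by the VISIT 7 scan and appears in no summary table. The Week 24 count is conditioned on not having been withdrawn for bone loss, and no planned table gives the number per arm who ever lost more than 7%.

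The displaced scan alone matters little: fewer than one woman per arm in every scenario has a loss above 7% seen only there. The stronger reason to act is the missing ever-lost count, 35–63 per arm in these scenarios against 30–47 shown at Week 24. Those figures depend wholly on assumed inputs, and the top of the range needs the most extreme of them. The window logic depends only on the SAP text, with one reservation: the Handling Rules for Analysis Data, which decide what data are acceptable, are a separate document not available here. The primary efficacy conclusion is unaffected.

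**What to change.** In SAP 7.11.5.1 add two rows by arm, for BMD percent change and T-score:

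1. **Last on-treatment scan:** the latest scan up to Follow-up Day 14, whatever its visit window.
2. **Lowest post-baseline scan:** report the existing below -7% category on this row, with all women who have any post-baseline DXA as the denominator.

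State in SAP 7.1.3 that the closest-day rule does not apply to these rows. Leave the by-visit tables and all clinical stopping rules as they are.

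The cost is a few lines of SAP text and two table rows from scans already collected. It should be settled before unblinding, so that the choice of a worst-value summary cannot be questioned later. There are two drawbacks: the reported number with more than 7% loss may be larger, and the last-scan row mixes treatment durations, so it should be read beside the by-visit rows. Priority is low.
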